8.1. Summary of Safety Analyses

As shown in Table 11, safety analyses will be performed over the 205MS303 Treatment period for the 205MS301-303 safety population, the 205MS203-303 safety population, and the 205MS302-303 safety population, respectively. For the 205MS301-303 safety population, results will be summarized by treatment group in the 205MS301 study and for all subjects combined. For the 205MS203-303 safety population, results will be summarized for all subjects combined. For the 205MS302-303 safety population, results will be summarized for all subjects combined. Sections below include more details about these analyses.

Table 11: Summary of populations for safety analyses over the 205MS303 Treatment Period

Population	Statistical Methods
205MS301-303 safety population	AEs, AEs of special interest, lab data, and vital signs will be descriptively summarized by treatment group in the 205MS301 study, and for all subjects combined.
205MS203-303 safety population	AEs, AEs of special interest, lab data, and vital signs will be descriptively summarized for all subjects combined.
205MS302-303 safety population	AEs, AEs of special interest, lab data, and vital signs will be descriptively summarized for all subjects combined.

8.2. Clinical Adverse Events

All treatment-emergent events in 205MS303 study will be included in the evaluation of safety. A treatment emergent event is defined as any event that either occurs or worsens in severity after the first dose of DAC HYP treatment in 205MS303 study. Events starting after permanent discontinuation of study drug will be included provided the start date was within 180 days of the last dose. Unless explicitly stated otherwise, analyses of adverse events will be limited to treatment emergent events in the 205MS303 study. If treatment emergence cannot be determined due to incomplete or partial start and/or end dates, the event will be considered to be 205MS303 treatment emergent.

Adverse events will be coded using the Medical Dictionary for Regulatory Affairs (MedDRA) version 16.1. In general, the incidence of treatment emergent adverse events will be presented by system organ class (SOC) and preferred terms (PT) but other classifications may be used.

The number and percentage of subjects with at least one event, at least one severe event and at least one study-drug related event will be presented. The incidence of adverse events classified by the appropriate system organ class and preferred terms will be summarized by severity and overall. If a patient experiences an event more than once with varying severity during the study, he/she will be counted only once with the maximum severity within each system organ class/preferred term. Events leading to study withdrawal and/or treatment discontinuation will be summarized.

In general, for the 205MS301-303 safety population, adverse events will be summarized by treatment group in the 205MS301 study and for all subjects combined. For the 205MS203-303 safety population, adverse events will be summarized for all subjects combined. For the 205MS302-303 safety population, adverse events will be summarized for all subjects combined.

Any deaths that occurred during the study will be listed and relevant information including timing of the death relative to study treatment, concomitant medications, the investigator assessment of the cause of death will be provided.

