1.1. Primary Objective and Endpoints

The primary objective of the study is to assess the safety and tolerability of long-term treatment with DAC HYP monotherapy in subjects who completed Study 205MS301, Study 205MS203, or Study 205MS302.

The primary endpoints of this study are incidence of adverse events (AEs) and incidence of serious AEs (SAEs).

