The design of Study 205MS303 is provided in [Figure 1](#). Approximately 1500 subjects will enroll in this study. This includes approximately 1200 subjects who completed Study 205MS301. Additionally, approximately 300 subjects from the other DAC HYP extension studies (205MS203 [SELECTED] and 203MS302 [OBSERVE]) will be eligible to enter Study 205MS303 at Week 144 of Study 205MS303 (Study 205MS301, Study 205MS203, and Study 205MS302 have been referred to as parent studies in the protocol).

All subjects will receive the same dose of DAC HYP as received in the parent studies; i.e., 150 mg by a subcutaneous (SC) injection every 4 weeks. The duration of DAC HYP treatment is up to approximately 5 years, or until availability of commercial product (whichever is sooner). Note that per sponsor discretion, the study was closed early and dosing was terminated by March 30th, 2018.

Figure 1: Study Design for 205MS303 study

¹Subjects who do not enter Study 205MS303 will complete post-dosing safety follow-up visits per the parent study protocol.

	
Protocol 205MS303 Statistical Analysis Plan for the Interim Analysis
	
Final Version 3.0

--	---	--

3. Schedule of Events

Table 1: Schedule of Activities: Baseline Through Week 84 for Subjects Enrolling From Study 205MS301 Into Study 205MS303

Note: If study treatment is temporarily suspended or withheld for abnormal liver function tests (LFTs), LFTs must be re-evaluated as specified in Protocol Section 11.7.2. A window of ± 4 days applies to all the visits.

Tests and Assessments ^{1,2}	Week 0/ Day 1 Baseline Visit ³	Week 4 ± 4 days	Week 8 ± 4 days	Week 12 ± 4 days	Week 24 ± 4 days	Week 36 ± 4 days	Week 48 ± 4 days Start Year 2	Week 60 ± 4 days	Week 72 ± 4 days	Week 84 ± 4 days
Informed Consent	X									
Confirm Eligibility	X									
Medical History Update, including Tobacco Use	X									
Physical Exam	X			X	X		X		X	
Vital Signs (Pre-dose)	X			X	X		X		X	
Weight	X									
Hematology	X			X	X		X		X	
Blood Chemistry (except LFTs)	X			X	X		X		X	
Liver Function Tests ⁴		Liver function testing to be performed within the previous 32 days (see Protocol Section 14.4.3)								
Liver Function Tests at Central Laboratory ^{4, 5}	X	X	X	X	X	X	X	X	X	X
Thyroid Function Panel	X									
DAC HYP Concentration Assessment	X			X	X		X			
Serum Biomarker Sample	X			X	X		X			
Urine Biomarker Sample	X						X			
RNA Assessment	X			X	X		X			
DNA Collection (Optional) ⁷										

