Table 5: Schedule of Activities: Post-Treatment Safety Follow-Up

Tests and Assessments	Post-Treatment Safety Follow-Up ¹				
	Follow-up Visit 1 8 weeks after last dose ±10 days	Follow-up Visit 2 12 weeks after last dose ±10 days	Follow-up Visit 3 16 weeks after last dose ±10 days	Follow-up Visit 4 20 weeks after last dose ±10 days	Follow-up Visit 5 (Final Study Visit) 24 weeks after last dose ±10 days
Physical Exam		X			X
Vital Signs		X			X
Hematology		X			X
Blood Chemistry (except LFTs)		X			X
Liver Function Tests at Central Laboratory ^{2, 3}	X	X	X	X	X
Anti-Drug Antibody Sample ⁴					X
Urine Pregnancy Test					X
DAC HYP Concentration Assessment ⁴					X
EDSS					X
Physician Global Assessment Scale	Performed only in subjects with ongoing cutaneous AEs (see Protocol Section 11.7.3)				
Concomitant Therapy and AEs	Monitor and record throughout the study.				
Protocol Compliance and DAC HYP Accountability	Monitor and record throughout the study.				

¹Post-treatment follow-up is required for all subjects. An End of Treatment Visit (Week 240) is performed 4 weeks (±4 days) after the subject's last dose of DAC HYP (see Table 4). Therefore, monthly monitoring of LFTs occurs for 6 months after the last DAC HYP dose has been administered. The Follow-up Visit 4 (20 weeks after last dose) is added under protocol version 5.

²ALT/SGPT, AST/SGOT, alkaline phosphatase, total bilirubin, and GGT only.

³For subjects with elevated LFTs, this should be performed as soon as possible and then at least weekly until stabilization (see Protocol Section 11.7.2).

Table 6: Schedule of Activities: Unscheduled Assessments

Tests and Assessments	Unscheduled Assessments			
	Unscheduled Relapse Assessment Visit (within 72 hours of symptoms)	Unscheduled Hepatic Assessment Visit ¹	Unscheduled Dermatology Assessment Visit ^{2,3}	Unscheduled PK/PD Visit ⁴
Cutaneous Event Assessment (Rash characteristics and Anatomic distribution), including Physician Global Assessment Scale			X	
Physical Exam	X	X	X	
Vital Signs	X	X	X	
Hematology				X
Liver Function Tests ⁶		X		X
Comprehensive Hepatic Panel ⁷		X		
Urinalysis	X			
Whole Blood Sample for PK/PD Assessments ⁸				X
EDSS ⁹	X			
Photographs ¹⁰			X	
Skin Biopsy ¹⁰			X	
Concomitant Therapy and AEs	Monitor and record throughout the study.			
Protocol Compliance and DAC HYP Accountability	Monitor and record throughout the study.			

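### AE incidence, a primary endpoint, is planned only as whole-period percentages although follow-up runs from one dose to about five years, and Section 8.2 names no overall SAE summary

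*SAP*

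**What the plan says.** Section 1.1 of the SAP sets the aim to "assess the safety and tolerability of long-term treatment with DAC HYP monotherapy" and continues: "The primary endpoints of this study are incidence of adverse events (AEs) and incidence of serious AEs (SAEs").

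Section 8.2 gives the summary measure for treatment-emergent events: "The number and percentage of subjects with at least one event, at least one severe event and at least one study-drug related event". It adds incidence by system organ class and preferred term, counting a subject once at the worst severity. Section 8.3 reports incidence for each AE group in Table 12 and repeats this for serious events where appropriate. Section 8.6 does the same by subgroup. Events leading to withdrawal or discontinuation are to be summarised, with no measure named.

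Follow-up is unequal by design:
- One dose in 205MS303 puts a subject in the safety population (Section 5.1).
- Subjects from 205MS203 and 205MS302 "will be eligible to enter Study 205MS303 at Week 144 of Study 205MS303" (Section 2).
- Table 4 lets 205MS301 subjects already in safety follow-up after Week 144 restart at Week 156.
- Section 2 also records that "the study was closed early and dosing was terminated by March 30th, 2018".
- Events count up to 180 days after each subject's own last dose (Section 8.2).

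Elsewhere the SAP does use time. Section 7.2 divides relapses by days of follow-up and also reports them by year or by 48-week interval. Section 7.9 annualises unscheduled visits. Section 6.3 computes time on study per subject but does not link it to AEs.

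**The concern.** The share of subjects with at least one event rises with the time they are watched. When follow-up varies from months to years, one percentage mixes the risk with the length of observation, and it hides when events occurred. For a study whose stated purpose is long-term safety, those are the two things a reader needs to separate. The SAP separates them for relapses, a secondary endpoint, but not for AE incidence, a primary one.

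A secondary objective in Section 1.2 covers the safety of switching from IFN β-1a. A whole-period percentage merges the first year after the switch with later years, so early risk after the switch cannot be seen.

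SAEs have a further gap. The Section 8.2 sentence covers any, severe and drug-related events. Severe is not the same as serious, so the second primary endpoint has no overall summary stated there.

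**Working it through.** The SAP gives no event rate, sample size calculation or power figure, so there is no stated figure to reproduce. The check asks what percentage the planned summary would show if the underlying risk were identical.

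**Follow-up windows, from the SAP**

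Table 5, footnote 1: "An End of Treatment Visit (Week 240) is performed 4 weeks (±4 days) after the subject's last dose of DAC HYP". The last scheduled dose is therefore at about Week 240 − 4 = Week 236. Entry at Week 144 leaves 236 − 144 = 92 weeks. Adding the 180-day window of Section 8.2:
- One dose: 180 / 365.25 = 0.49 years
- 205MS203 or 205MS302 entrant: (92 × 7 + 180) / 365.25 = 824 / 365.25 = 2.26 years
- 205MS301 entrant: (236 × 7 + 180) / 365.25 = 1832 / 365.25 = 5.02 years

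These are planned maxima. Early closure shortens them by amounts the SAP does not give.

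**Expected percentage at equal risk**

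Formula: 1 − exp(−rate × years). The rates are assumptions, shown as a range.

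| Assumed rate per year | One dose, 0.49 y | 203/302 entrant, 2.26 y | 301 entrant, 5.02 y | Ratio, 301 to 203/302 |
|---|---|---|---|---|
| 0.02 | 1.0% | 4.4% | 9.5% | 2.16 |
| 0.05 | 2.4% | 10.7% | 22.2% | 2.08 |
| 0.10 | 4.8% | 20.2% | 39.4% | 1.95 |
| 0.5 | 21.8% | 67.6% | 91.9% | 1.36 |
| 1.0 | 38.9% | 89.5% | 99.3% | 1.11 |

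At the high rates the ratio shrinks because both percentages approach 100%, where they no longer discriminate.

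**Effect of discontinuation within one cohort**

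A simulation used 400,000 subjects per setting, with exponential discontinuation (assumed), dosing capped at 236 weeks and 180 days added. First-event rates divide subjects with an event by person-time to the first event or the end of that window.

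| Discontinuation per year | Crude %, true rate 5 per 100 y | First events per 100 y | Crude %, true rate 10 per 100 y | First events per 100 y |
|---|---|---|---|---|
| 5% | 20.1 | 4.99 | 36.1 | 10.04 |
| 15% | 17.0 | 5.02 | 30.6 | 10.00 |
| 30% | 13.5 | 5.01 | 24.6 | 9.94 |

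With unchanged risk the crude figure moves by a factor of up to 20.1 / 13.5 = 1.49, while the rate stays at its true value.

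**The case against.** Much of the opposing case stands and limits the claim.

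- A reader might infer that the SAP sets up a biased comparison between cohorts. It does not. Sections 5.1 and 8.1 tabulate each cohort separately, the analyses are generally descriptive, and no pooled or cross-cohort safety comparison is planned. The two-fold figure describes what happens if someone sets two separate tables side by side.
- The one planned side-by-side display is prior IFN β-1a against prior DAC HYP in the 205MS301 cohort. These groups share the planned start, the maximum follow-up and the closure. The SAP gives no discontinuation figures, so bias between them cannot be asserted.
- A reader might infer that SAEs are planned as crude percentages only. Section 8.2 plans no overall SAE summary at all. Serious events appear in Section 8.3 and in the Section 8.6 subgroups. A total could be rebuilt by adding the two age subgroups, but that is not a stated primary summary.
- Hepatic risk is not wholly invisible over time. Section 8.5 summarises quantitative laboratory values, including liver tests, by visit, and part of its liver text is redacted. Deaths are listed with their timing, and exposure is summarised. None of this gives AE or SAE incidence over time, and the Section 8.2 text as shown has no redaction.
- Rates do not cure everything. A single rate summarises risk well only if the hazard is roughly constant. Comparisons between cohorts would still carry differences in earlier DAC HYP exposure and the selection of parent-study completers.

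**Conclusion.** The point holds as a weakness of method. AE incidence and the AEs of interest, including their serious events, are planned only as whole-period subject counts and percentages. Those depend on how long subjects were followed and cannot show risk changing over time. Separately, Section 8.2 leaves the SAE primary endpoint without an overall summary.

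The size depends on the event. At an assumed equal constant hazard of 0.02 to 0.10 per year, the planned maxima alone produce about a two-fold difference between cohorts. The ratio falls to 1.36 at 0.5 and 1.11 at 1.0 per year, so it is small for any-AE incidence if most subjects have an event. Between the two 205MS301 groups it is nil unless discontinuation differs. An extreme assumed contrast of 5% against 30% per year gives about 1.5-fold.

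The result rests on assumed rates and on planned rather than actual follow-up. It does not support a claim that any planned comparison is already known to be biased.

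**What to change.** Keep the percentages and state an overall SAE summary in Section 8.2.

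**Rates.** For any AE, SAEs, AEs leading to discontinuation and the key Table 12 groups (at least hepatic events, serious infections, serious skin reactions and immune-mediated disorders), add subjects with a first event per 100 subject-years with 95% CI. Show these by cohort and by prior 205MS301 treatment. Person-time should run from the first 205MS303 dose to the earliest of first event, end of study participation, or 180 days after last dose. That matches the AE counting window in Section 8.2. The 205MS303 Treatment Period in Section 5.3 ends at the last available measurement before 180 days, so using it as the denominator would not match the numerator.

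**Timing.** For SAEs and the key groups in the 205MS301 cohort, add incidence by 48-week interval since first 205MS303 dose, with numbers at risk. Label it time since 205MS303 entry. It equals time on DAC HYP only for the prior IFN β-1a group, because the others were already treated.

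**Cost.** SAP wording and some extra tables from data already collected. The two later cohorts together number about 300 (Section 2), so intervals there would be sparse; for that reason the interval tables are limited to the 205MS301 cohort.

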8.3. Adverse Events of Interest

The following groups of adverse events are of special interest due to potential mechanism of action, therapeutic class, or prior clinical experience with DAC HYP. The groups of interest, and the MedDRA-based or other criteria utilized to determine the events falling into each group are described in the following table.

Table 12: Adverse Events of Special Interest

	Group	Criteria	Summary by
1.	Infections and serious infections	SOC of Infections and Infestations	PT and seriousness
2.	Serious skin reactions	SOC of Skin and Subcutaneous Tissue Disorders; SMQ for Severe cutaneous adverse reactions (SMQ) [narrow terms only]	PT
3.	Hepatic events	Sublevel SMQ of Drug Related Hepatic Disorders – Comprehensive Search under the SMQ of Hepatic Disorders	SOC/PT
4.	Colitis	HLT of Colitis (Excl Infective), primary or secondary pathway	PT
5.	Autoimmune haemolytic anaemia	SMQ Haemolytic disorders	PT

6.	Lymphadenopathy	Customized search of the following PTs: abdominal lymphadenopathy, adenoiditis, angiolymphoid hyperplasia with eosinophilia, autoimmune lymphoproliferative syndrome, Castleman's disease, hilar lymphadenopathy, histiocytic necrotising lymphadenitis, lymph node pain, lymph node palpable, lymphadenitis, lymphadenocyst, lymphadenopathy, lymphadenopathy mediastinal, lymphatic disorder, lymphoid tissue hyperplasia, lymphoproliferative disorder, lymphoproliferative disorder in remission, myeloproliferative neoplasm, paratracheal lymphadenopathy, persistent generalised lymphadenopathy, PFAPA syndrome, retroperitoneal lymphadenopathy	SOC/PT
7.	Depression and suicide	SMQ of Depression and Suicide/Self Injury	PT
8.	Malignancies	Sublevel SMQ of Malignant or Unspecified Tumours under the SMQ of Malignancies, then confirmed as malignancies following medical review.	PT
9.	Hypersensitivity	SMQ of Hypersensitivity (narrow search terms)	SOC/PT
10	Anaphylactic reactions	SMQ of Anaphylactic Reactions (narrow search terms) SAEs within 24 hours after dosing	PT
11	Angioedema	SMQ of Angioedema (narrow search terms)	PT
12	Opportunistic infections	Customized search including selected preferred terms	PT
13	Lymphopenia	PTs: Lymphopenia; lymphocyte count abnormal; Lymphocyte count decreased; B-lymphocyte count decreased, Leukopenia, Differential white blood cell count abnormal; Lymphocyte percentage decreased, Lymphocyte percentage abnormal	SOC/PT per severity
14	Immune mediated disorders	HLGT of Autoimmune Disorders, primary or secondary pathway, plus the additional 1 PT of Coombs Negative Hemolytic Anemia, minus the 2 PT of Multiple Sclerosis and Optic Neuritis	SOC/PT
15	Sarcoidosis	High Level Term: Acute and chronic sarcoidosis and the Preferred Term of Heerfordts syndrome	PT

	Protocol 205MS303 Statistical Analysis Plan	Final Version 1.0
---	--	--------------------------

The incidence of adverse events in each group will be summarized for the 205MS301-303 safety population, the 205MS203-303 safety population, and the 205MS302-303 safety population, respectively; where appropriate, the analysis will be repeated for serious events.

8.4. Additional Efficacy and Safety Endpoints

Additional efficacy and safety endpoints described in this section will be analyzed for the 205MS301-205MS303 study.

8.4.1. Beck Depression Inventory Score

Depression scores will be calculated according to the BDI-II manual, Second Edition. Subjects with a total score of 18 or higher will be considered as positive for depression. For the 205MS301-303 safety population, BDI-II scores, their change from DAC HYP Baseline, and the proportion of subjects positive for depression will be summarized by visit in the 205MS303 study. If there are more than 2 responses for the same question, the response with the highest (worst) rating will be used in the analysis.

Note that Beck depression inventory score is not collected for patients enrolled from 205MS203 or 205MS302 study to the 205MS303 study.

8.4.2. Treatment Satisfaction Questionnaire for Medication

Summary statistics for the treatment satisfaction questionnaire for medication, by 205MS301 treatment group, will be provided for baseline and post-baseline visits of the 205MS303 study for the 205MS301-303 ITT population. The responses to the questionnaire may be grouped properly.

Note that treatment satisfaction questionnaire for medication is not collected for patients enrolled from 205MS203 or 205MS302 study to the 205MS303 study.

8.4.3. MSFC Score

There are 3 components to the MSFC:

- (1) the average scores from the 4 trials on the 9-hole peg test (9HPT) (the 2 trials for each hand are averaged, converted to the reciprocals of the mean times for each hand and then the 2 reciprocals are averaged);
- (2) the average scores of the 2 Timed 25-Foot Walk trials;
- (3) the number correct on the Paced Auditory Serial Addition (PASAT) 3 test.

The MSFC z-score is calculated by creating z-scores for each component of the MSFC, as explained below, and averaging them to create an overall composite score, i.e.,

MSFC z-score = $(Z_{25\text{-foot-walk}} + Z_{9\text{HPT}} + Z_{\text{PASAT}3})/3$, where Z_{xxx} refers to Z-scores.

	
Protocol 205MS303 Statistical Analysis Plan
	
Final Version 1.0

---	--	--

A z-score represents the number of standard deviations a subject's test result is higher ($z > 0$) or lower ($z < 0$) than the average test result ($z = 0$) of the reference population.

Calculation for Raw and Z-score for each component

The following describes the scoring, rules for missing value imputation for each component.

Timed 25-Foot Walk Z-score Calculation

The Z-score is calculated as in the following formula:

$$Z_{25\text{-foot-walk}} = (-1) * \frac{((t_1 + t_2) / 2) - MEAN(reference)}{SD(reference)},$$

where t_1 and t_2 are the time (in seconds) from the two trials, and the mean (reference) and SD (reference) are the mean and standard deviation respectively, of baseline values for the reference population. For scores to be comparable with scores in 205MS301, the same reference population is used. Baseline values for the reference population are the values at the 205MS301 baseline for the reference population (205MS301 ITT population). The same is applicable to 9HPT and PASAT 3 Z-scores.

Timed 25-Foot Walk Raw Score Calculation

The row score is calculated as in the following formula:

$$R_{25\text{-foot-walk}} = (t_1 + t_2) / 2,$$

where t_1 and t_2 are the time (in seconds) from the two trials.

Missing Value Handling for Timed 25-Foot Walk

For missing baseline and post-baseline values, if a subject is missing only one trial for any post-baseline visit, then the score from the non-missing trial will be used to calculate both the Z-score and Raw score, unless the reason for the missing score is due to MS related physical limitation or other physical limitations. If reason is due to one of the reasons listed above, the score for that specific trial will be back-calculated using the Z-score value of -13.7 (see formula below), and then the average of the two trials will be taken. The steps outlined above will remain the same.

If both scores from the two trials are missing for any post-baseline visit due to MS related physical limitation or other physical limitations, (based on the missing data algorithm suggested by the MSFC algorithm) the subject will be given a Z-score of -13.7 for the Timed 25-Foot walk. The Row-score will be back-calculated using the following formula:

	
Protocol 205MS303 Statistical Analysis Plan
	
Final Version 1.0

---	--	---

$$R_{25\text{-foot-walk}} = MEAN(reference) + 13.7 * SD(reference).$$

9HPT Z-score Calculation

Z-score for the 9HPT is calculated as in the following formula:

$$Z_{9HPT} = \frac{\left(\left(\frac{1}{(t_{11}+t_{12})/2} + \frac{1}{(t_{21}+t_{22})/2} \right) / 2 \right) - MEAN(reference)}{SD(reference)},$$

where t_{11} , t_{12} , t_{21} , t_{22} are the time (in seconds) taken to complete for dominant hand trial 1, dominant hand trial 2, non-dominant hand trial 1, and non-dominant hand trial 2, respectively. The mean (reference) and SD (reference) are the mean and standard deviation, respectively, of reference population's baseline score.

9HPT Raw Score Calculation

Raw-score for the 9HPT is calculated as in the following formula:

$$R_{9HPT} = \left((t_{11} + t_{12}) / 2 + (t_{21} + t_{22}) / 2 \right) / 2$$

where t_{11} , t_{12} , t_{21} , t_{22} are the time (in seconds) taken to complete for dominant hand trial 1, dominant hand trial 2, non-dominant hand trial 1, and non-dominant hand trial 2, respectively.

Missing Values for 9-hole Peg Test

For missing baseline and post-baseline values, if a subject is missing only one trial for any post-baseline visit (for either dominant or non-dominant hand), then the score from the non-missing trial will be used to calculate both scores, unless the reason for the missing score is due to MS related physical limitation or other physical limitations. If reason is due to one of the reasons listed above, the score for that specific trial will be imputed with a raw score value of 777, and then the average of the two trials will be taken. The steps outlined above will remain the same.

The missing data algorithm suggested by the MSFC manual will be used to impute missing values. If both scores from either hands are missing for any post-baseline visit, due to MS related physical limitation or other physical limitations, then the subject will be given a Row-score using a value of 777. The Z-score will be calculated with the following formula:

$$Z_{9\text{HPT}} = \frac{\frac{1}{777} - \text{MEAN}(\text{reference})}{\text{SD}(\text{reference})},$$

PASAT 3 Z-score Calculation

For the PASAT 3, the z-score for each subject at each time-point will be created by subtracting the reference population's baseline mean score on the PASAT 3 from the subject's PASAT 3 score and dividing by the baseline SD on the PASAT 3 of the reference population, i.e.

$$Z_{\text{PASAT3}} = \frac{\text{PASAT 3 raw score} - \text{MEAN}(\text{reference})}{\text{SD}(\text{reference})},$$

and PASAT 3 raw score = # of items correct.

Missing Values

For missing post-baseline values, if a subject is missing the PASAT 3 score due to MS disease limitations, then a score of 0 will be imputed as the *raw score*. Missing baseline values will not be imputed.

For the 205MS301-303 ITT population, actual value, change and percentage change from the 205MS301 baseline in the MSFC z-scores as well as for each individual MSFC component z-scores will be summarized by 205MS301 treatment group in Combined Study Period (by study visit in 205MS301 and 205MS303 studies). Similarly, for the 205MS301-303 ITT population, the MSFC z-scores as well as for each individual MSFC component z-scores with change from 205MS303 baseline will be summarized by 205MS301 treatment group in the 205MS303 Treatment Period (by study visit in 205MS303 study).

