1.2. Secondary Objective and Endpoints

Secondary objectives of this study in this study population are as follows:

- To describe MS-related outcomes, including MS relapse, disability progression, MS lesion formation, and patient-reported impact of MS, following long-term treatment with DAC HYP
- To assess the long-term immunogenicity of DAC HYP administered by prefilled syringe (PFS)
- To assess the safety, tolerability, and efficacy of switching to DAC HYP in subjects previously on long-term treatment with interferon β -1a (IFN β -1a) in Study 205MS301

The secondary endpoints of this study are as follows:

- Relapse outcomes: annualized relapse rate (ARR), and proportion of subjects who relapse
- Sustained disability progression defined by at least a 1.0-point increase on the Expanded Disability Status Scale (EDSS) score from a baseline EDSS ≥ 1.0 that is sustained for 24 weeks, or at least a 1.5-point increase on the EDSS from a baseline EDSS < 1.0 that is sustained for 24 weeks
- Magnetic Resonance Imaging (MRI) outcomes: total number and volume of new or newly enlarging T2 hyperintense lesions, Gd-enhancing lesions, T1 hypointense lesions, and brain volume change on brain MRI
- Change in Multiple Sclerosis Functional Composite (MSFC) score
- Change in EDSS score
- Change in Symbol Digit Modalities Test (SDMT) score
- Change in 3 Second Paced Auditory Serial Addition Test (PASAT 3) score
- Proportion of subjects who are free from disease activity.

[figure not shown]
- Change in Multiple Sclerosis Impact Scale-29 (MSIS-29) physical and psychological scores
- Change in quality of life as assessed by the European Quality of Life, 5 dimensions and European Quality of Life, Visual Analogue Scale (EQ-5D and EQ-VAS)
- Change in direct health resource utilization (HRU; hospitalizations, emergency room visits, and unscheduled neurologist visits)
- Change in treatment satisfaction as assessed by the subject
- Change in subject productivity as assessed by the Health Related Productivity Questionnaire (HRPQ)
- Changes in clinical laboratory assessments (hematology and blood chemistry)
- Local tolerability as assessed by subject-reported injection site pain, Visual Analogue Scale (VAS) and clinician injection site assessments
- Incidence of anti-drug antibodies (ADAs) to DAC HYP over time
- Incidence of neutralizing antibodies (NAbs) to DAC HYP over time

2. Study Design

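### MSFC scoring imputes extreme walk and peg-test values for non-MS physical limitations, and no planned analysis shows how much those cases matter

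*SAP*

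**What the plan says.** SAP section 8.4.3 forms the MSFC z-score as the plain average of three component z-scores. Its rules for missing trials are:

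- **Walk, both trials missing.** The condition reads "If both scores from the two trials are missing for any post-baseline visit due to MS related physical limitation or other physical limitations". What follows from it is an extreme value: "the subject will be given a Z-score of -13.7 for the Timed 25-Foot walk". The raw time is back-calculated as the reference mean plus 13.7 reference SDs. The stated basis is: "based on the missing data algorithm suggested by the MSFC algorithm".
- **Walk, one trial missing.** The default is to use the completed trial. For either kind of limitation, however, "the score for that specific trial will be back-calculated using the Z-score value of -13.7", and the two trials are averaged.
- **9HPT, one trial missing.** For the same two reasons, the missing trial is set to 777 and averaged with the completed one.
- **9HPT, both trials missing.** If this is "due to MS related physical limitation or other physical limitations, then the subject will be given a Row-score using a value of 777", and the z-score is computed from 1/777. The SAP credits the MSFC manual for this rule.
- **PASAT 3.** After baseline, "if a subject is missing the PASAT 3 score due to MS disease limitations, then a score of 0 will be imputed" (on the raw scale). No other reason triggers imputation.

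Section 5.4 sets a general rule of no imputation unless a section says otherwise. Section 1.2 lists change in MSFC as a secondary endpoint, under an objective that begins "To describe MS-related outcomes, including MS relapse, disability progression". The MSFC and component z-scores are summarised by visit and by 205MS301 treatment group, both over the Combined Study Period and within the 205MS303 Treatment Period. The SAP plans no sensitivity analysis for MSFC.

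**The concern.** The second reason in the walk and peg-test rules is stated as an alternative to MS-related limitation, so it covers causes unrelated to MS. Nothing confines it to lasting causes. A temporary injury that prevents the test would be scored exactly like inability caused by MS, and would look like recovery once the subject could do the test again. The EDSS endpoint in section 7.4.1 guards against transient worsening by requiring 24-week persistence; the by-visit MSFC summaries have no such guard.

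The single-trial rule goes further, because it discards the default of using a valid observation from the same visit. The PASAT 3 rule shows that the same section can tie an extreme score to MS alone.

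At stake are the mean and spread of a named secondary endpoint, and of its walk and peg-test components, at each MSFC visit.

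**Working it through.** **Inputs from SAP section 8.4.3:** imputed walk z = -13.7; weight of each component = 1/3; 9HPT raw value = 777. **From section 2:** about 1200 subjects from 205MS301. **Not in the SAP:** how often tests are missed for non-MS limitations, the SD of the MSFC, and the reference mean and SD. Values used for these are assumptions.

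**1. The plan's own figure.** Put R = MEAN + 13.7 × SD into Z = -(R - MEAN)/SD. This gives Z = -13.7 for any reference mean and SD, so the back-calculation is consistent.

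**2. One subject, walk.** The comparison is with a subject whose walk z would otherwise be 0.
- Both trials missing: MSFC shift = -13.7/3 = -4.57.
- One trial missing, the other at the reference mean: walk z = -13.7/2 = -6.85; MSFC shift = -6.85/3 = -2.28.

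**3. A visit mean, both walk trials missing.** For a share p of subjects imputed for non-MS reasons, the walk mean shifts by -13.7p and the MSFC mean by -13.7p/3. The SD component added to the MSFC is √(p(1 - p)) × 13.7/3.

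| Assumed p | Walk mean | MSFC mean | Added SD component |
|---|---|---|---|
| 0.5% | -0.069 | -0.023 | 0.32 |
| 1% | -0.137 | -0.046 | 0.45 |
| 2% | -0.274 | -0.091 | 0.64 |

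If the MSFC SD were otherwise 0.5 (assumed), at p = 1% it would become √(0.25 × 0.99 + 0.206) = 0.67. One case in a prior group of about 600 (1200 split equally, an assumption) moves that group's mean MSFC by -4.57/600 = -0.008.

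**4. One subject, 9HPT.** Assume a reference mean reciprocal time of 0.040 to 0.050 and an SD of 0.008 to 0.012. Then z = (1/777 - mean)/SD runs from about -3.2 to -6.1, an MSFC shift of about -1.1 to -2.0. These figures apply when the whole test is scored as 1/777. The wording of the rule can be read to allow that when only one hand is unusable. If only the affected hand were set to 777, z would be about -1.6 to -3.0.

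**5. After restriction.** If missing trials due to non-MS limitations are not imputed, the artificial shift from these cases is 0.

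**The case against.** The strongest case for the plan has five parts.

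- **The rule is deliberate and sourced.** The SAP attributes it to the MSFC algorithm and manual. Neither is at hand, so the documents do not support a claim that the SAP departs from the instrument's own scoring. Section 5.4 allows specified exceptions, so the general no-imputation rule is not contradicted either. This stands.
- **Comparability.** Section 8.4.3 keeps the 205MS301 reference population so that scores can be compared across studies, and the Combined Study Period tables use visits from both. Changing the main derivation for 205MS303 alone would mix two scoring rules in one table. This stands, and it is why the main derivation should stay.
- **PASAT 3 differs in kind.** Physical limitation is a natural reason to miss a walking or hand test and a less obvious one for serial addition. This weakens the contrast but does not explain why non-MS incapacity should count as MS disability.
- **Attributing cause is imperfect.** An injury may follow an MS-related fall, and leaving it missing would drop real functional loss. This is a reason to show both scorings.
- **Impact is limited.** The analysis is descriptive, the primary endpoints are AEs and SAEs, and Table 1 schedules MSFC in 205MS303 only at baseline and Weeks 12, 24 and 48. The rates above are assumed. This stands as a limit on importance.

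A reader might also infer that the rule biases the comparison of former IFN β-1a and DAC HYP subjects. The documents do not support that: nothing suggests that non-MS limitations occur at different rates in the two groups. A chance imbalance could produce a difference, but that is not a systematic bias.

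**Conclusion.** The point holds as a moderate one. As written, section 8.4.3 scores non-MS incapacity on the walk and peg tests like severe MS disability, even when one trial was completed, and nothing in the plan would reveal it. The effect on one subject is large: about -4.57 on the MSFC with both walk trials missing, and about -2.28 with one missing and the other at the reference mean. The effect on a visit mean depends on a rate that the SAP does not give. At an assumed 0.5% to 2% of subjects with both walk trials missing for non-MS reasons, and a walk z otherwise near 0, the mean MSFC falls by 0.023 to 0.091. The SD is the more sensitive summary.

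Two stronger readings should be avoided. The imputed value is not always the worst score available: a single missing trial is averaged with the observed one, and the SAP does not call -13.7 or 777 a floor. Nor do the documents show that the current derivation is an error to be replaced.

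**What to change.** Keep the current derivation as the main MSFC scoring, and add a pre-specified second analysis of the MSFC and component z-scores:

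- Restrict -13.7 and 777, in both the single-trial and both-trials rules, to MS-related limitations.
- For other physical limitations, use the observed trial if there is one; otherwise leave that component and the composite missing at that visit.
- Apply this identically to 205MS301 and 205MS303 visits in the Combined Study Period.
- Report the number of imputed cases by reason, visit and prior treatment group, so that a reader can see whether the two scorings could differ materially.

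The cost is one extra set of tables, some programming that reaches back to 205MS301 visits, and a few more missing values in the added analysis. It depends on the reason for a missing trial being recorded in separate categories. The wording of the rule implies this, but the SAP does not state it, so it should be confirmed against the case report form.
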